## **I. Hypotheses and Specific Aims**

**Aim 1.** Evaluate the efficacy of the Cogito Companion as an upstream suicide prevention intervention.

**Hypothesis 1.1.** Participants allocated to the Cogito Companion will report significantly fewer episodes of distress and less distress over the course of the study (Outcome Questionnaire-45; OQ-45) compared to those allocated to the Active Control group.

**Hypothesis 1.2.** Among those with episodes of clinically meaningful distress, those allocated to the Cogito Companion will more rapidly engage in treatment (medical record review and Client Services Receipt Inventory-EU-Revised; CSRI-EU-R) to address such symptoms versus those allocated to the Active Control group.

**Hypothesis 1.3.** Participants allocated to the Cogito Companion will report significantly fewer episodes of and less severe depressive (Patient Health Questionnaire-9; PHQ-9) and post-traumatic symptoms (Post Traumatic Stress Disorder Checklist-5; PCL-5), and suicide-related thoughts (Beck Scale for Suicide Ideation; BSS, Columbia-Suicide Severity Rating Scale Screener; C-SSRS Screener), as well as overall increased perceived physical/psychological health functioning (Rand 36-Item Health Survey; SF-36) over the course of the study compared to those allocated to the Active Control condition.

**Aim 2.** Evaluate the acceptability and feasibility of the Cogito Companion among military personnel (Sailors).

**Aim 2.1.** Acceptability of Cogito Companion will evaluate based on participant satisfaction (CSQ), participant engagement in application-related activities (e.g., leaving voice recordings), and time spent on the application. Acceptability refers to the suitability of an intervention from the perspectives of the participants.

**Aim 2.2.** Feasibility of Cogito Companion will be evaluated based on participant retention and accrual, and number and type (minor, moderate, severe) of technical challenges noted during implementation. Feasibility refers to the ease of implementation.

**Exploratory Aim.** Identify patterns of distress, depressive symptoms, post-traumatic symptoms, suicide-related thoughts, and perceived physical and psychological health functioning over the course of the study among the entire sample, as well as within the Cogito Companion and Active Control groups.

## **II. Background and Significance**

Research suggests that Naval personnel experience concerning levels of anxiety, stress, and suicidal ideation while deployed. Moreover, the post-deployment period has been shown to be particularly risky in terms of suicidal thoughts and behaviors. Given this, novel, non-stigmatizing, and portable upstream prevention strategies are needed to evaluate behaviors, moods, and symptoms over time, particularly during periods of transition. Whereas regular and frequent monitoring by health diaries can be unreliable, the development of smartphone technology has created accessible means to record, store, display, and monitor (self and other) health information. In specific, technology developed by the Cogito Corporation (Cogito

Companion), and evaluated by members of this research team, has the capability to enable military personnel self-care and facilitate early identification of risk for suicide. However, research is needed to establish evidence for this type of intervention.

**Suicide Risk and Periods of Transition.** Research suggests that periods of transition are associated with changes in mental health, including increased risk for suicidal ideation and behavior. Additionally, studies have shown that increased risk for death by suicide following a transition is often closely tied to psychosocial stressors, including loss of employment, romantic relationships, onset of illness, or declines in physical health. Timing of transitional periods may also be of import. For example, Warner and colleagues found three time periods of significantly increased risk for suicidality among United States (US) Soldiers over a 15-month deployment cycle. The first period occurred in the second month and was hypothesized to be a result of separation from important social relationships. The second was after six months in theater, which was hypothesized to be related to feelings of isolation after returning from leave. Perhaps most pertinent to this proposed study, the third period was near the end of the Soldier's deployment and thought to be related to exposure to increased stressors on the home front. Highlighting the need for increased focus on the period of transition from military service to Veteran status, the President recently signed an Executive Order entitled, "Supporting Our Veterans During Their Transition from Uniformed Service to Civilian Life". Within the order, the Departments of Defense (DoD), and Veterans Affairs (VA), as well as Homeland Security were directed to develop a plan to ensure that those separating from service receive necessary mental health care. However, current strategies (e.g., Post Deployment Health Assessment) have proven to have limited utility in identifying those whose symptoms develop in the weeks and months following periods of transition (e.g., redeployment to the continental United States [CONUS]). As such, exploration of novel strategies (e.g., smartphone based mobile applications [app]), is indicated.

Historically, suicide prevention efforts have largely focused on individuals known to be at high risk. Although this continues to be an important strategy, efforts are also required "to keep [military personnel] from ever reaching the point of contemplating or attempting suicide", by early identification of increased risk and rapid intervention. To date, limited research has been conducted to evaluate such upstream approaches, particularly among military personnel. Identification of evidence-based upstream interventions is necessary to decrease risk among military personnel during periods of transition.

**Smartphone Technology and the Cogito Companion.** Smartphone technology can be used to record, store, and monitor (self and other) vital information regarding suicide risk. Specifically, the Cogito Corporation has developed a secure, privacy-compliant mobile app (Cogito Companion). The Cogito Companion was designed to collect and interpret social signals underlying smartphone behaviors via usage, to non-invasively collect, transfer, integrate, analyze, and report objective behavioral measures of psychological distress. Measurements of location, call, and text patterns are fed into machine learning algorithms to compute behavioral measures. These measurements provide proxies for behavioral and cognitive components of depression, mood, and anxiety disorders. Over time, these patterns may provide markers for changes in occupational and social functioning. For example, when a Service member is functioning well, he or she is likely to have a routine level of communication and spend certain hours of the day at home versus at work, or out and about. However, with the onset of mental health symptoms, he/she is more likely to spend increasing amounts of time at home, and limit communication. Adaptive algorithms combine these elements over time to derive behaviorally driven changes in these patterns.

In addition, individual users are prompted by the Cogito Companion to complete standardized psychological measures (see below) and to record short (a few seconds to 10 minute) audio diaries. Using vocal analytics, recordings can be transformed into predictive metrics of depressed mood. Specifically, the recording is analyzed regarding the manner in which people speak, rather than what they say. An analysis of vocal qualities, rather than content, allows the technology to predict depressed mood from short field-based audio recordings, while remaining objective to topic, demographic, or even language spoken. Participants will be asked to enter audio diaries every two weeks, which will be used to produce an additional real-time, longitudinal, and clinically validated measure of depressed mood. Data regarding social signals

underlying smartphone behaviors, as well as from the measures and audio diaries, are displayed in the Clinician Dashboard (see below).

### **III. Preliminary Studies/Progress Report:**

**Development of Cogito Algorithms.** Serving as a contractor to the Defense Advanced Research Program Agency (DARPA), Cogito gathered an extensive dataset of individual trauma survivors' mobile data. With the goal of developing mobile phone behavioral health monitoring for military personnel, the Cogito team ran a 3-month study of 100 participants. The participants, both Veteran and civilian, were enrolled for 12 weeks during which time they each carried a mobile phone equipped with a research app. The research app passively monitored, on an intermittent fixed schedule, probe readings from sensors hardwired into the current generation mobile phone. These sensors included call logs, short message service (SMS) logs, locational pattern changes, acceleration, and battery levels. During the study, participants also filled out weekly self-report metrics around mood disorder symptomatology, left weekly audio diaries, and met with a clinician for a Structured Clinical Interview DSM-IV (SCID-IV) at both intake and exit dates of the study. Cogito used structured machine learning to create models, which took in, as inputs, these raw data streams and predicted the clinical level assessment of symptomatology. Each model outputs a score from 0-100, indicating the probability of presence of the behavioral component of mental health. The model uses a week of data to create a score, and updates on a daily basis. Cogito researchers also met with clinical stakeholders to assess the most useful and actionable means of presenting feedback to patients.

**Civilian RCT.** Among civilians, a 171 person two-arm randomized clinical trial (RCT) was conducted to compared use of the Cogito Companion to standard care in an integrated behavioral health patient-centered medical home setting. In this National Institute of Mental Health funded clinical trial, the PHQ-9 was the primary outcome. Results showed a statistically significant decrease in this score for patients who received the Companion relative to those who did not. While these findings were not focused on military personnel or upstream suicide prevention, they bolster the hypothesis that Cogito Companion could have a positive effect on improving PHQ-9 outcomes in our study population.

**VA Pilot Study.** Members of this research team ([name], [name], [name]) conducted a pilot study to assess the acceptability and feasibility of Cogito Companion among military Veterans. Participation in the study included a baseline visit, using the mobile app for three months, and one follow-up visit. Participants were sent surveys every two weeks while using the app, and were outreached as needed for clinical concerns or administrative and/or technical issues. One hundred and six Veterans were enrolled in the pilot study, and 85 have completed the study protocol. Initial results support both the feasibility and acceptability of the intervention among Veterans from all cohorts. With an eye towards the population of interest for this proposal, the following data is from Veterans who served in Operation Enduring Freedom/Operation Iraqi Freedom/Operation New Dawn (OEF/OIF/OND; N=53). The vast majority of these individuals reported enjoying using the app with half rating their level of enjoyment as "Yes, a lot", another 43% reporting "Yes, a little", and only 7% reporting "No, not at all". Per the study protocol, acceptability was established apriori as 70% of participants scoring 24 or greater on the Client Satisfaction Questionnaire (CSQ). In this sample, 81% scored above this cut off; thereby suggesting overall acceptability. Qualitatively, OEF/OIF/OND Veterans reported that they liked the ability to self-monitor their symptoms. For example, one participant noted "it allows me freedom to sign in and say what I want when I want or I mean [audio diary], give information I want to or need to when I want to". Another Veteran described, "it just reminded me to take a step back, to breathe. To understand there's always people there that are willing to help you and talk to you". In addition, some participants discussed how specific app functions provided motivation to be more social and active, such as, "it [app] reminded me...of the need to get out of the house on a daily basis. Not just sit and take the pill-pain pills". These data suggest that the intervention will be acceptable to Active Duty Sailors.

## IV. Research Methods

### A. Outcome Measure(s)

Aim 1. Outcome Questionnaire (OQ-45). The OQ-45 is a psychometrically sounds 45-item measure designed to evaluate key areas of mental health functioning, including symptom distress. It is a widely-accepted tool for identifying, tracking, and measuring behavioral health treatment outcomes.

Client Services Receipt Inventory-EU-Revised (CSRI-EU-R). This is a measure which queries regarding use of inpatient hospital, outpatient hospital, community based-day services, as well as primary and community care contacts. In addition to validating care documented in electronic medical records, it will be used to identify care received outside of the MHS. In a recent systematic review of self-report measures, use of this tool was noted as being a valid method for data collection on healthcare utilization.

Patient Health Questionnaire-9 (PHQ-9)\*. This is a frequently used and psychometrically sound self-report measure of depression.

Posttraumatic Stress Disorder Checklist 5 (PCL-5)\*. The PCL-5 is a self-report measure used to evaluate post traumatic symptom severity. Criteria is based on Diagnostic and Statistical Manual of Mental Disorders-5 criteria. Items are rated on a 5-point Likert scale.

Beck Scale for Suicidal Ideation (BSS)\* is the self-report version of the Beck Scale for Suicide Ideation. Concurrent validity (comparing patient and psychiatrist ratings) was reported as .90 ( $p < .001$ ) and internal reliability was similarly high ( $\alpha = .93$ )

Rand 36-Item Health Survey is a 36-item psychometrically sound quality of life outcome-measure that yields perceived physical and mental health functioning summary scores.

The Columbia-Suicide Severity Rating Scale (C-SSRS) Screener is a screening measure, administered by a clinician or electronically, that assesses for suicidal ideation and attempt behavior based on established definitions. The C-SSRS screener assesses intensity of suicidal ideation, specifically asking about frequency, duration, intrusiveness, controllability, and deterrents, as well as suicide-related behavior, such as actual attempts and aborted attempts.

Aim 2. Client Satisfaction Questionnaire (CSQ). The CSQ is an eight-item questionnaire with adequate reliability and validity, which has frequently been used to evaluate standard community mental health care. Items are scored on a Likert-type scale where '1' indicates the lowest degree of satisfaction and '4' the highest.

General. MSRC Standard Demographic Form. Information will be gathered on topics such as participant age, gender, race/ethnicity, education, military service, and combat exposure.

University of Washington Risk Assessment Protocol-Revised (UWRAP). The UWRAP will be used during clinical outreach phone calls to facilitate risk identification. The UWRAP has been recommended by National Institute of Mental Health and has been used in over 20 years of research.

Self-Help Mobile Application Survey. The study team will develop a brief survey to identify applications that military personnel may use for mental health and wellness, and may include brief items such as the purpose of the app, and estimated amount of time (i.e., minutes) they interacted with these mobile apps. Participants will be specifically asked about mHealth Tools developed by the National Center for Telehealth & Technology), as well as any additional apps (free text field). Some examples include: the Virtual Hope Box, Breathe2Relax, and the T2 Mood Tracker. Those in the experimental arm will complete this survey at the beginning and end of the study. Participants allocated to the Active Control arm will respond to these survey questions every two weeks.

MSRC Common Data Elements (CDEs). The Military Suicide Research Consortium's (MSRCs) questionnaire includes shortened measures of the following: current and past suicide risk, lethality and intent of past suicide attempts, hopelessness, thwarted belongingness, anxiety sensitivity, posttraumatic stress disorder symptoms, traumatic brain injury, insomnia, and alcohol abuse. All studies funded by MSRC are required to include the CDEs in their assessment protocol.

COVID-19 Questionnaire. The brief self-report asks participants about the impact of the COVID-19 pandemic and stressors related to the pandemic. Questions are also taken from the Fear of Illness and Virus Evaluation (FIVE) form.

*Additional Data Sources.* Mobile Apps. In addition to data obtained from the measures outlined above, data from those allocated to the Cogito Companion group will be captured via the mobile app including: the number of phone calls made and received, and the length of those calls; the number of text messages sent and received; how frequently the mobile app is used; and which features of the app the participant chooses to view.

For those in the Active Control arm, MyCAP data will be captured regarding app usage and information accessed (e.g., links to wellness apps) using the Self-Help Mobile Application Survey developed by the study team (see description above, as well as measures pushed regarding their mental health. Measures demarcated with an \* above will be sent every two weeks (see Figure 1 below).

*Technical Challenges (Implementation Data).* For those in both groups, data will also be collected regarding technical challenges faced by participants such as: forgotten passwords; no individual model scores; and, not completing biweekly surveys. Moreover, for individuals in both conditions, we will capture information regarding research staff outreach (Administrative, Clinical).

*Military Health System (MHS) Data.* Study participant medical usage (including medical and mental health) data (e.g., dates of visits, hospitalizations), Current Procedural Terminology [CPT Codes], International Classification of Diseases codes, Ninth Revision and Tenth Revision [ICD-9/10]) will also be obtained from the MHS. This will include information regarding all visits to a MHS facility during and 1 month post the study period (a total of four months). Likely data systems of interest include the MHS Data Repository (MDR)/Military Health System Mart (M2), as well as the Mental Health Research File.

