## **B. Description of Population to be Enrolled**

Inclusion Criteria. 1) Member of the Naval Surface or Aviation Forces; 2) Age: 18-55 years at the time of enrollment; 3) History of at least one deployment with return to permanent station within the past 36 months, or stationed outside the Continental United States with permanent change of station (PCS) to the Continental United States within the past 36 months, or any PCS move within the past 36 months or on initial command duty assignment; 4) Ability to provide verbal and electronic informed consents; 5) Ownership of smartphone; and 6) Willingness to use smartphone and personal data plan to participate.

Exclusion Criteria. 1) Having an iPhone (until the Cogito Corporation releases the iOS version of the Cogito Companion app).

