**Table 1. Measures and Administration**

| Measure                                                  | Domain                         | Baseline | During Intervention (Biweekly) | Follow-up Survey |
|----------------------------------------------------------|--------------------------------|----------|--------------------------------|------------------|
| Beck Scale for Suicidal Ideation (BSS)                   | Suicidal ideation              | X        | X                              | X                |
| Client Satisfaction Questionnaire (CSQ)                  | Satisfaction with intervention |          |                                | X                |
| Client Services Receipt Inventory-EU-Revised (CSRI-EU-R) | Health care utilization        | X        | X                              | X                |
| Columbia-Suicide Severity Rating Scale (C-SSRS) Screener | Suicidal ideation and behavior | X        | X                              | X                |
| MSRC Common Data Elements                                |                                |          |                                | X                |
| MSRC Standard Demographic Form                           | Demographics                   | X        |                                | X                |
| Outcome Questionnaire (OQ-45)                            | Psychological Distress         | X        | X                              | X                |
| Patient Health Questionnaire-9 (PHQ-9)                   | Depression                     | X        | X                              | X                |
| Posttraumatic Stress Disorder Checklist 5 (PCL-5)        | PTSD                           | X        | X                              | X                |
| Rand 36-Item Health Survey                               | Quality of life                | X        | X                              | X                |
| Self-Help Mobile Application Utilization Survey          | Use of readily available Apps  | X*       | X**                            | X*               |
| COVID-19 Questionnaire                                   |                                | X        | X                              | X                |

\*All study participants; \*\*Those allocated to the Active Control arm only

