**C-SSRS Screener Monitoring.** Clinical team members will review responses to the C-SSRS and conduct outreach based upon recent and/or current suicidal ideation and/or suicidal or self-harm behaviors. Specifically, we will outreach if the participant positively endorses thinking about how they may kill themselves, have had thoughts of killing themselves with intention of acting on these thoughts, and/or if they've started to work out details of how to kill themselves.

Using the same clinical thresholds described above, the Cogito app will send an automatic notification to the participant regarding their scores, as well as resources (e.g., Military and Veterans Crisis Line, Military OneSource, Military Health System provider contact information [individualized data entered by participant or study team]).

**Cogito Model Score Monitoring.** Model scores are presented both in number and color format (Figure 4). Red indicates scores 39 or below, yellow indicates scores between 40 and 79, and green indicates scores between 80 and 100. The higher the score, the "healthier" the individual's behaviors. Any drastic daily change in score (+/- change of 20) and/or two scores less than 20 may prompt a clinical outreach call.

**Active Control.** Participants randomized to the Active Control group will download MyCAP and have access to resources housed within this app for a three-month period post-consent. Participants will be provided information regarding the mHealth Tool apps, and provided basic information on how to download the apps. As noted above, participants will be provided biweekly surveys as listed in Table 1. Participants will get one notification when surveys are available. If surveys are not completed, participants may be sent a reminder to complete the surveys via MyCAP automatic reminder or the in-app messaging feature.

**Clinical Research Staff Outreach – Active Control.** Clinically-trained research team members will monitor the MyCAP dashboard each business day one time per day (excluding federal holidays and weekends); however, outreach will solely be based on survey data or lack thereof.

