between the groups and each median will be reported with 95% CIs. Treatment engagement is operationalized as a visit with any medical or mental health provider in which a mental health related ICD code is identified. and will be determined by medical record review. Additionally, the total number of mental health visits calculated from the CSRI-EU-R will be modeled using a Poisson or Negative Binomial regression model to estimate the difference in number of visits between the groups over the course of the study. The model will be set up similarly to the OQ-45 model. Hypothesis 1.3 is similar to hypothesis 1.1 such that we wish to look at episodes of depressive symptoms (PHQ-9), post-traumatic symptoms (PCL-5) and suicide-related thoughts (BSS) as well as severity of each over the course of the study. We also wish to look at perceived physical and psychological health functioning (RAND SF-36) over the course of the study. The methods employed to address hypothesis 1.1 will be utilized to estimate the difference in number of episodes of each outcome (excluding the SF-36) as well as the difference in AUC for each outcome. Zero-inflated negative binomial regression will be considered for the BSS if a large proportion of the participants do not exhibit suicidal thoughts and transformations will be considered for the AUC BSS analysis, given that it is likely to be highly skewed. Cutoffs for episodes of depressive/post traumatic symptoms, and suicidal thoughts are  $\geq 10$  (PHQ-9),  $\geq 33$  (PCL-5), and  $\geq 2$  (BSS), respectively.

***Aim 2.*** We will assess the proportion of participants who find the Cogito Companion acceptable, defined as  $\geq 70\%$  of participants scoring  $\geq 24$  on the CSQ. The proportion of Cogito Companion participants with a CSQ score of  $\geq 24$  will be calculated with a 95% CI. Additionally, the proportion of participants engaging in activities will be reported with a 95% CI as well as the median (range) amount of time spent on the application. Feasibility will be measured by the proportion of Cogito Companion participants who complete treatment and reasons for termination will be examined.

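### Hypothesis 1.2 counts routine visits by sailors already in mental health care as engagement, so it measures time to the next mental-health-coded visit rather than treatment sought because of distress

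*Protocol*

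**What the plan says.** Protocol section I states the hypothesis: "Among those with episodes of clinically meaningful distress, those allocated to the Cogito Companion will more rapidly engage in treatment". It adds that the purpose of that treatment is to deal with the distress.

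Protocol section IV.F defines the event: "Treatment engagement is operationalized as a visit with any medical or mental health provider in which a mental health related ICD code is identified". The event "will be determined by medical record review". The comparison is of Kaplan-Meier median times by group, each with a 95% CI. No time zero is stated, and nothing requires the visit to be new or linked to the distress episode.

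Protocol section IV.A, on MHS data, gives the record window: "This will include information regarding all visits to a MHS facility during and 1 month post the study period (a total of four months".

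The only exclusion in section IV.B is phone type: "Exclusion Criteria. 1) Having an iPhone (until the Cogito Corporation releases the iOS version of the Cogito Companion app". Section IV.C stratifies randomisation by gender, force and phone type, not by care status.

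Table 1 has the row "Client Services Receipt Inventory-EU-Revised (CSRI-EU-R) | Health care utilization", marked at baseline, biweekly and follow-up. The stated uses of this questionnaire are to validate records and find care outside the MHS (section IV.A), and to count mental health visits over the study (section IV.F).

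The SAP reprints this analysis. Its revised aims do not list Hypothesis 1.2, but its opening paragraph says the original analysis plan continued to be followed.

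**The concern.** Take a sailor with standing appointments who scores 64 or more on the OQ-45 in week 4 and attends a visit in week 5 that was booked before enrolment. The plan records engagement within a week, whatever the app did. What is estimated is time to the next mental-health-coded visit, which mixes scheduled follow-up with new engagement.

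Two consequences follow. If the app speeds up new engagement but not booked appointments, routine events common to both arms dilute the contrast. If the share already in care differs between the distressed subsets, an apparent difference can arise with no effect at all. Those subsets form after randomisation, so balance in them is not guaranteed.

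**Working it through.** **Record window.** Access to either app lasts three months after consent (section IV.C; for the control arm, "have access to resources housed within this app for a three-month period post-consent"). 3 + 1 = 4 months, which reproduces the stated total and leaves 4 − 4 = 0 months before enrolment. The plan gives no power, event count or effect size for Hypothesis 1.2, so there is nothing else to reproduce.

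**Illustration A.** All rates are assumptions. A share p of the distressed is already in care, and their next visit is uniform on 0 to g weeks, with g = 2 or 4, unaffected by the app. The rest engage at h = 0.03 per week (control) or 0.045 (Cogito), a true ratio of 1.5. Observation lasts 12 weeks.

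- Probability of an event if not in care: F = 1 − exp(−12h) = 1 − exp(−0.36) = 0.302 (control) and 1 − exp(−0.54) = 0.417 (Cogito).
- Mean time at risk if not in care: F/h = 10.08 and 9.27 weeks. If in care: g/2.
- Event rate = [p + (1 − p)F] / [p·g/2 + (1 − p)F/h]. At p = 0.4 and g = 4: control 0.581/6.846 = 0.0849, Cogito 0.650/6.363 = 0.1022, ratio 1.20.
- In-care share of control events = p / [p + (1 − p)F]. At p = 0.4: 0.4/0.581 = 69%.
- A median later than g is ln[2(1 − p)]/h, so the ratio of medians is 0.045/0.03 = 1.5. At p = 0.4: 0.182/0.03 = 6.1 and 0.182/0.045 = 4.05 weeks.

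| In care | Rate ratio (g = 2; 4) | Control events from in-care | Medians in weeks, control vs Cogito | Ratio of medians |
|---|---|---|---|---|
| 0% | 1.50; 1.50 | 0% | neither reached by week 12 | n/a |
| 20% | 1.31; 1.31 | 45% | 15.7 (beyond week 12) vs 10.4 | 1.5 |
| 40% | 1.21; 1.20 | 69% | 6.1 vs 4.05 | 1.5 |
| 50% | 1.17; 1.17 | 77% | 1.9 vs 1.8 (g = 2); 3.6 vs 3.4 (g = 4) | 1.03; 1.05 |
| 60% | 1.14; 1.13 | 83% | 1.6 vs 1.6 (g = 2); 3.1 vs 3.0 (g = 4) | 1.02; 1.03 |

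The ratio of medians holds at 1.5 while p ≤ 1 − exp(0.045g)/2, that is, up to 45% for g = 2 and 40% for g = 4. Above that it falls quickly. The rate ratio is diluted at every non-zero share.

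**Illustration B.** Again assumed: 90 days; next routine visit exponential with mean 28 days; new entry in control q = 10% or 20%, so h = −ln(1 − q)/90; true hazard ratio 1.5. Survival is S(t) = p·exp(−t/28) + (1 − p)·exp(−ht).

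- In-care share of control events = p(1 − exp(−90/28))/(1 − S(90)). At p = 0.2 and q = 10%: 0.192/0.272 = 71%. At p = 10, 20 and 30%: 52, 71 and 80% (q = 10%), or 35, 55 and 67% (q = 20%).
- Ratio of 90-day cumulative hazards, ln S(90) for Cogito over control: 1.25, 1.16 and 1.12, or 1.34, 1.25 and 1.20.
- Neither median is reached in 90 days at shares up to 30%. At 40% with q = 20% the medians are 88 vs 68 days, ratio 1.28, so irregular visit spacing dilutes the medians somewhat earlier than in A.

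**Imbalance with no true effect.** An in-care share of 25% (Cogito) against 20% (control) gives an apparent ratio of 1.13 to 1.14 in A and 1.19 in B (q = 10%). A share of 30% against 20% gives 1.28 to 1.30 and 1.40.

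**Restricting to those not in care.** In A the 12-week event proportions are 30% and 42%. Both are below 50%, so neither median is reached.

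**The case against.** The strongest reply is that the hypothesis speaks of engaging in treatment, not of first entry. Time to the next coded visit after distress is a legitimate, broader quantity, and someone already in care might also be prompted to come in sooner. Both illustrations set that effect to zero by assumption. This stands: the planned result is interpretable as time to the next coded visit.

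A reader might go further and infer that early events would be dominated by routine visits and that the medians would merely reflect appointment intervals. The documents do not support that. They give no in-care share, visit spacing or engagement rate. In illustration A the contrast in medians is unaffected up to 40% in care.

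A reader might also infer that an imbalance in prior care would be undetectable. It would be invisible in the MHS extract, but service use is asked at baseline. The plan also compares baseline clinical characteristics and considers those that differ significantly as confounders. The visit-count model, set up like the OQ-45 model, would inherit that route. The cover is partial: baseline care is not named, the rule acts only on a significant difference, and a Kaplan-Meier estimate takes no covariates. No balance rule removes dilution, which occurs with equal shares.

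Finally, Hypothesis 1.2 is not one of the two powered primary hypotheses and is missing from the revised aims. That lowers its weight but does not retire it, since the SAP reprints the analysis and says the original plan was followed.

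**Conclusion.** The point holds as a mismatch between hypothesis and event. With any coded visit counted, no record look-back and no separation of those already in care, the analysis estimates time to the next mental-health-coded visit. A null result could hide faster new engagement, and a positive one could reflect unequal prior care in the distressed subset. It does not follow that the planned analysis is uninterpretable.

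The size cannot be derived from the documents. Under the assumed rates, a true ratio of 1.5 becomes roughly 1.1 to 1.3 on a rate or cumulative-hazard scale at in-care shares of 10% to 60%. The ratio of medians is materially affected only as the share approaches half or more (somewhat earlier if visit spacing is irregular). Because the hypothesis is secondary and the repair uses data already collected, this is a change that should be made, not a threat to the trial's main conclusions.

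**What to change.** Before analysis, add four rules to the SAP.

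1. Classify each participant as in or not in mental health care at baseline from the baseline CSRI-EU-R, supplemented by a pre-enrolment MHS look-back if approvals allow.
2. State time zero, and stratify the time-to-engagement comparison by that status, for example with a stratified log-rank test or Cox model. Report each stratum.
3. For those not in care, report cumulative engagement by the end of follow-up, because the median may not be reached.
4. Adjust the CSRI-EU-R visit-count model for baseline visits.

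Without the look-back, this costs only SAP wording and programming. The look-back needs a longer date range in a data request already planned, and consent and waiver wording to cover it. The drawbacks are small strata and, without the look-back, a baseline status that rests on self-report with a recall period the documents do not give.
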